### **12.1. Stratification by Site**

The impact of treatment is not expected to vary over site. Unless otherwise indicated, analyses will not be presented by site. Many, if not most, sites are expected to enroll a small number of subjects.

### **12.2. Unscheduled and/or Repeated Laboratory Results**

Unscheduled or repeated laboratory results will be placed together in a separate listing and discussed in a dedicated section of the clinical study report. If any of these values are to replace the values in planned procedures to acquire analysis tables, all such decisions will be justified in the clinical study report.

### **12.3. Handling of Early Termination Visit Information**

Early termination visit data for safety variables will be analyzed at the closest scheduled visit. If the closest visit has valid data, the early termination data will be assigned to the next available visit.

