8.2.4 Early Discontinuation of Subjects

In the event that a subject is prematurely discontinued from the study, efforts should be made to collect all clinical and laboratory data as scheduled for End of Treatment visit (See [Section 8.4.1](#)) and the subject should be followed up for safety, as appropriate. See [Section 8.5.6.2](#) for details on following up on AEs. In addition, the Investigator should complete and report, as thoroughly as possible, the reasons for withdrawal.

Subjects who discontinue from the study will be treated as per the Investigator's discretion and standard of care for children with CPP.

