8.6.5 Part A, Visit 3 (~Month 3/Week 12 ± 7 days)

1. Query subject or parent: “How have you felt in the last two weeks?” or “How has your child felt in the last two weeks?” Complete [Table 4](#)
2. Vital signs - measured prior to any blood draws
3. AE and concomitant medications assessments
4. Physical Examination—directed
5. Tanner stage
6. Height and weight
7. Blood samples for basal LH, FSH, testosterone/estradiol concentrations PRIOR to the GnRHa stimulation
8. Blood sample for basal serum leuprolide concentrations PRIOR to the GnRHa stimulation
9. GnRHa stimulation: aqueous leuprolide acetate 20 µg/kg body weight administered SC
10. Blood samples for LH, FSH, testosterone/estradiol concentrations 30 ± 5 minutes AFTER the GnRHa stimulation
11. Schedule/confirm next visit

NOTE: Subjects who do not show adequate suppression of LH concentration to <4 mIU/mL (after GnRHa stimulation test) will be discontinued.

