9.2.5 Accounting for Missing Data

Imputation of missing data will not be performed for baseline, efficacy, and safety endpoints.

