## 12. IMPUTATION AND MISSING DATA

Unless otherwise indicated, imputation of missing data will not be performed for baseline, efficacy and safety variable values. Each table containing an analysis that reflects an outcome at a given time point in the study will contain only subjects in the analysis population under examination who have data available at that time point.

If a missing concentration datum is surrounded by non-missing values, interpolation will be used in the calculation of AUC, Cmax and Tmax. Otherwise, the nearest non-missing point in time will be used.

If missing date and time values are evident in data not used to develop PK parameters, the following missing date and time algorithm may be applied.

For partial start date/time:

- If the year is unknown, then the date will not be imputed and will be assigned a missing value.
- If the month is unknown, then:
  - If the year matches the year of the dose of study drug date, then the month and day of the dose of study drug date will be imputed.
  - Otherwise, 'January' (01) will be assigned.
- If the day is unknown, then:
  - If the month and year match the month and year of the dose of study drug date, then the day of the dose of study drug date will be imputed.
  - Otherwise, '01' will be assigned.
- If the day is unknown, then:
  - If the month and year match the month and year of the dose of study drug date, then the day of the dose of study drug date will be imputed.
  - Otherwise, '01' will be assigned.
- If the time is unknown, then:
  - If the date (day, month, and year) matches the date of the dose of study drug date, then the time of the dose of study drug time will be imputed.
  - Otherwise, '00' will be assigned.
- For partial stop date/time:
  - If the year is unknown, then the date will not be imputed and will be assigned a missing value.
  - If the month is unknown, then 'December' (12) will be assigned.
  - If the day is unknown, then the last day of the month will be assigned.
  - If the time is unknown, then the last time of the day will be assigned.

If time to an event were needed when only the hour, and not the minutes, are reported for the time of the event, then the minutes will be set to zero.

Any deviations from the implementation of the missing date and time algorithms will be documented in the dataset documentation and final report.

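### SAP Section 12.3 sets no window and can tabulate early-termination safety values at a later visit the child never attended, against the available-data rule in SAP Section 12

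*SAP*

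**What the plan says.** SAP Section 12.3 has two steps and covers safety variables only. First: "Early termination visit data for safety variables will be analyzed at the closest scheduled visit". Second: "If the closest visit has valid data, the early termination data will be assigned to the next available visit". It does not define *closest* or *next available*, and gives neither a window nor a separate early-termination row.

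SAP Section 12, of which 12.3 is a subsection, says of every table reporting an outcome at a given time point that it "will contain only subjects in the analysis population under examination who have data available at that time point". The sentence before that reads: "Unless otherwise indicated, imputation of missing data will not be performed for baseline, efficacy and safety variable values". Protocol Section 9.2.5 is shorter: "Imputation of missing data will not be performed for baseline, efficacy, and safety endpoints".

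On what is collected at discontinuation, Protocol Section 8.2.4 says "efforts should be made to collect all clinical and laboratory data as scheduled for End of Treatment visit". That set includes vital signs, weight, a complete physical examination, hematology, chemistry and urinalysis (Protocol Section 8.6.11). Protocol Section 8.6.5 provides one route to a discontinuation soon after a completed visit: "Subjects who do not show adequate suppression of LH concentration to <4 mIU/mL (after GnRHa stimulation test) will be discontinued".

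**The concern.** A child who leaves between two visits has normally completed the earlier one. If the final assessment is nearer to that visit, the slot is taken and the fallback applies. No attended slot remains open, so the natural destination is a visit after the child has left. The table then shows a real measurement under the wrong time label, and the child is counted at a visit that never took place.

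The Week 12 rule makes this foreseeable. LH is assayed at a central laboratory (Protocol Section 8.4.13), so the result would normally arrive after the Visit 3 vital signs are recorded, and the early-termination visit follows.

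The outputs at stake are the by-visit safety summaries. Protocol Section 9.2.6 summarizes laboratory results for each study visit and vital signs at each time point, and SAP Table 5 adds weight and physical examination. SAP Section 18.2 defines the n shown as subjects with non-missing values, so each re-labelled value raises n at a visit the child did not attend.

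**Working it through.** The plan gives no figure on this point, so there is none to reproduce. The check applies the SAP 12.3 rule to the scheduled weeks.

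**Inputs (Table 1 in both documents).**
- Part A vital signs and weight: Weeks 0, 4, 12, 20, 24, 36, 44, 48.
- Part A hematology and chemistry after dosing: Weeks 4, 24, 48.
- Window for post-baseline visits: ±7 days.

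**Assumptions.** All earlier visits were attended with valid data, and *next available* means the next later visit.

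**Formula.** Let the assessment fall at week t between consecutive visits a and b. If t − a < b − t, the closest visit is a. It is filled, so the value goes to b. Shift = b − t, which lies between (b − a)/2 and b − a.

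| Assessment | Closest visit | Destination | Shift |
|---|---|---|---|
| Vital signs, Week 13 | Week 12, filled | Week 20 | 20 − 13 = 7 weeks |
| Vital signs, Week 26 | Week 24, filled | Week 36 | 36 − 26 = 10 weeks |
| Hematology/chemistry, Week 26, visits judged per variable | Week 24, filled | Week 48 | 48 − 26 = 22 weeks |

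In days, 7 weeks is 49 and 10 weeks is 70, against a window of 7.

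**Range.** The Part A gaps for vital signs are 4, 8, 8, 4, 12, 8 and 4 weeks. The fallback therefore shifts them by just over 2 weeks (half of 4) up to just under 12. Judged per variable, the laboratory gaps are 24 − 4 = 20 and 48 − 24 = 24 weeks, so the shift runs from just over 10 weeks to just under 24.

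**First step.** If t is nearer to b, the value also goes to b, which is empty and was not reached, but the shift is then less than half the gap. A window is therefore needed for both steps.

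**Against Section 12.** A child assessed at Week 13 who then left has no Week 20 vital signs. By the available-data sentence the child is not in the Week 20 table; by 12.3 the child is. Both cannot be followed.

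**The case against.** A reader might infer that 12.3 contradicts the no-imputation rule, or amounts to carrying a value forward. The documents do not support that. One observed measurement receives one visit label; no value is created and none is repeated at later visits. The SAP's bar on imputation also opens with an exception for cases otherwise indicated, and 12.3 sits within the same section. Protocol Section 9.2.5 lacks the exception, but labelling an observed value is still not imputation. This objection stands, and the conflict is only with the available-data sentence.

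A reader might also infer that laboratory values taken just after Week 12 would be reported at Week 24. On the plain reading they would not. The closest visit to Week 13 or 14 is Week 12, where no hematology or chemistry is drawn, so the slot is empty and the first step places them there, 1 to 2 weeks off. Even judged per variable, Week 14 is a tie: 14 − 4 = 10 and 24 − 14 = 10. The Week 26 laboratory example is conditional too. Week 24 is closest and filled on either reading, but Week 48 follows only if the destination must be a visit that draws those tests; otherwise it is Week 36, a 10-week shift.

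The consequences are limited. Adverse events are tabulated by system organ class and preferred term, disposition reports terminations with reason and date, and all collected values are listed. Safety analysis is descriptive, and no decision rule uses by-visit safety means. All of that stands.

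Finally, assigning early-termination data to a scheduled visit is an accepted convention. That is fair for a value close to the visit. It does not justify assignment at any distance.

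**Conclusion.** The point holds as a small drafting fault in a stated rule. On its natural reading, SAP 12.3 labels observed early-termination safety values with visits after discontinuation. The examples give 7 and 10 weeks for vital signs, and 22 weeks for hematology and chemistry if visits are judged per variable. It conflicts with the available-data sentence in SAP Section 12. The effect is confined to timing and n in the by-visit summaries of vital signs, weight, laboratory tests and physical examination.

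This rests on earlier visits having been attended and on *next available* meaning a later visit. The SAP does not define the term, but no other reading is natural when the earlier slots are filled.

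The number of children affected cannot be derived. Taking the complement of the expected 85% to 90% suppression on 60 children gives 0.10 × 60 = 6 to 0.15 × 60 = 9. However, that expectation is not stated for the Week 12 test, and the synopsis describes the 60 as screened and/or enrolled. Nor can one say that most such values would come from treatment failures: Protocol Section 8.2.3 lists eight reasons for discontinuation and gives no split.

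**What to change.** Replace the SAP 12.3 rule with one that does the following:

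- Maps an early-termination safety value to a scheduled visit only if it falls within that visit's ±7-day window and the slot for that variable is empty.
- Otherwise reports it in a separate early-termination (last on-study) row, with its actual study day.
- Removes the *next available visit* step.

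Any remaining shift is then at most one week, and the rule agrees with the available-data sentence. A Week 13 value with Visit 3 already recorded would go to the early-termination row.

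The cost is SAP wording, one extra row per table and a slightly smaller n at later visits. No new data are needed. The change should be recorded in SAP Appendix 4 before the statistician examines the data, since SAP Section 4 treats only such changes as *a priori*.

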## **13. CDISC**

To meet recent current FDA Guidance (December 2014) on the submission of standardized study data, the study data will be formulated into data sets to provide transparency, traceability, and integrity of trial analysis results from the collection source. Reference is made to FDA Study Data Technical Conformance Guide (March 2015) for adherence to the FDA Guidancev. The observed study data will be mapped to the current CDISC Study Data Tabulation Model (SDTM) and serve as the source data from the trial. All study analyses will be completed using analysis data sets that are derived from the SDTM and follow the CDISC Analysis Data Model (ADaM) architecture.

### **13.1. Clinical Data – CDISC Study Data Tabulation Model (SDTM)**

Domains will be mapped to CDISC SDTM using Implementation Guide (IG) version 3.2 or higher. No derived data other than age and converted units of measure that will be analyzed are to be included in the SDTM domains. All SDTM domains will be fully documented with define documents (DEFINE.XML) and a reviewer's guide after database lock and final analyses are completed.

### **13.2. Analysis Data – CDISC Analysis Data Model (ADaM)**

All planned *a priori* and unplanned "post hoc" analyses will be completed using the ADaM data sets derived from the SDTM domains for this study. Analysis data sets will contain all derived study endpoints required for analyses, graphs and specifically designated listings. All analysis data sets will be fully documented with define documents (DEFINE.XML) and a reviewer's guide after database lock and final analyses are completed.

Additional analysis data sets may be developed to support unplanned analyses after database lock. The SAP will not be amended for additional analysis data sets defined for the study and these additional data sets will be documented in the define documentation completed after all analyses are completed for the trial and the clinical study report is written.

## **14. ADDITIONAL INFORMATION RELEVANT TO THE ANALYSES**

### **14.1. Protocol Deviations**

Protocol deviations will be summarized in a listing. Important protocol deviations are defined as deviations that could potentially bias the conclusion. A summary of the number and percentage of subjects with important deviations by deviation category will be provided. A listing of important protocol deviations by subjects and country will also be provided.

### **14.2. Safety**

#### **14.2.1. Concurrent Illness and Medical Conditions**

The number and percent of subjects with individual concurrent illness and medical histories will be summarized over all subjects in the safety population. Individual subject listings will also be provided for concurrent illness and medical history. The medical history data will be coded using the Medical Dictionary for Regulatory Activities (MedDRA) Version 18.0. A data listing of the body system, verbatim condition/abnormality/procedure, date of onset, and an indicator of continued presence will be provided. A summary table will be provided.

#### **14.2.2. Prior and Concurrent Medications**

The number and percent of subjects who took prior and concurrent medications will be summarized descriptively by the ATC class and preferred term as coded in the WHO-Drug dictionary overall subjects. Concomitant medications will be summarized similarly. Prior and concomitant medications will be summarized for the Safety Population. Prior and concomitant medication with the verbatim, ATC level 3 category, preferred term, indication, dosage, route, unit, frequency and start/stop dates of administration will be provided in the listings.

### **14.3. Subject Enrollment**

A summary of subject disposition will display the number of subjects who enrolled, who received study drug, and who remained in the study. Also included in this summary will be the number of subjects who terminated from the study by reason and termination date. Subject enrollment and disposition with reason for termination will be presented in a listing. Reasons for termination (discharge from the study) will also be present in a listing, ordered by primary reason for early termination, then by subject ID.

#### **14.4. Adverse Events**

Adverse events (AEs) will be coded using current MedDRA (ex. Version 18.0). Number and percent of subjects reporting AEs will be tabulated for the Safety population. Summaries will be presented by System Organ Class (SOC) and Preferred Term (PT), and further by severity and relationship to the investigational product. In summaries of severity, subjects who reported more than one event that are mapped to the same SOC and/or PT will be counted only once under the strongest severity. In summaries of relationship, subjects who reported more than one event that are mapped to the same SOC and/or PT will be counted only once under each applicable relationship.

All TEAEs will be listed individually by subject. In addition, a separate listing will be produced for AEs that are not treatment-emergent, where appropriate.

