Leuprolide acetate is also available as a suspension formulation for SC injection (under the brand name ELIGARD[®]), which is currently approved for palliative treatment of advanced prostate cancer (Product Insert-05/2014), up to a maximum dose of 45 mg administered every 6 months. The leuprolide acetate 45 mg in the study drug is in a controlled release injection solution formulation with the polymer Atrigel[™] and has been used extensively in over 1 million administrations for the treatment of prostate cancer.

Each different extended formulation of leuprolide acetate has different release characteristics to optimize the GnRHa activity. For example, clinical experience with leuprolide acetate has demonstrated prolonged testosterone suppression with daily administration of as little as 1 mg, or after administration in depot formulations at intervals of one month or longer ([Chrisp 1991](#)). The pharmacokinetics of GnRH agonists, includes an initial 'flare-up' of the pituitary-gonadal axis, followed by a reduced luteinizing hormone secretion by desensitization of pituitary GnRH receptors. During the first weeks of treatment, clinical signs of puberty, such as vaginal bleeding, may occur. This is a common initial effect of drugs with leuprolide acetate. The new signs/symptoms of puberty can continue beyond the second month of treatment. In the Package Insert for Eligard under Section 17 (Information for Patients), it includes information, as with other GnRH agonists, that patients may experience hot flashes (flares) after injection and in the first few weeks of treatment may also experience increased bone pain, increased difficulty in urination, and the onset or aggravation of weakness or paralysis and that these symptoms should be reported. Patients should also be told that the injection site may have transient burning/stinging, slight pain, bruising, and redness that are usually mild and reversible. Rarely allergic reactions do occur and should be reported immediately.

Benefits of leuprolide acetate for the treatment of CPP include increases to or restoration of projected adult height, and protection from the psychosocial harm associated with clinically significant early puberty ([Kim 2013](#)). Leuprolide acetate has been shown to be safe and effective during treatment periods from three months to one year at doses up to 20 mg/day in humans ([Yamanaka 1985](#)).

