8.5 Safety Evaluation

8.5.1 Safety Parameters

Safety parameters to be measured/assessed include eligibility assessments, medical history, vital signs, physical examinations, clinical laboratory tests, and pregnancy tests. Any abnormal hematology, serum chemistry, serum lipid, or urinalysis parameters considered clinically significant by the Investigator will be captured as AEs.

Subjects will be monitored throughout the study for AEs, as well as for changes in clinical status, vital signs, and laboratory data. Any non-serious AEs occurring from the time the ICF and Assent forms, if required, are signed until just prior to receiving the first injection of study drug will be considered as non-TEAEs unrelated to study drug administration.

Serious adverse events (SAEs) that occur as a result of study-mandated procedures during the time period after the ICF and Assent forms are signed, as appropriate, but prior to receiving the first injection of study drug will be collected but not designated as TEAEs.

In order to evaluate changes in the acute (within two weeks of administration) and chronic hormonal responses associated with GnRH antagonist treatments over time, subjects (or their parents/guardians) will be asked two weeks (14 days \pm 2 days) after every study drug administration (by telephone contact), and at each scheduled visit, the following question(s):

- How have you felt in the last two weeks?

or alternatively (if the parent or guardian is answering on behalf of the subject)

- How has your child felt in the last two weeks?

Investigators will record any adverse events that are reported at that time.

In addition the investigators will categorize the more specific responses that have been identified in the table ([Table 4](#)), which are often associated with GnRH antagonist injectable treatments. If the subject (or parent/guardian) does not report any condition (within the last two weeks) that fits into the [Table 4](#) categories, the Investigator will check the response that no conditions associated with GnRH antagonists were reported (“NO”). If any of the conditions reported by the subject (or parent/guardian) fit into one (or more) of the categories, then the Investigator will check “YES” for each applicable category. This reported information will be collected by completing [Table 4](#):

Table 4 GnRH Antagonist Evaluations

Any GnRH antagonist conditions reported?	Yes/No
If the answer is “Yes”, please categorize as described below:	

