8.5.5 Reporting of Adverse Events

All AEs that are observed by the Investigator or one of his/her medical collaborators, or reported by the subject, will be reported even if they are potentially attributable to unrelated medical

conditions or other medications the subject may be taking. The information recorded for AEs will include start date, a description of the AE, severity, causal relationship to Investigational Product/study drug, action taken, outcome of the event (including any treatment and/or hospitalization), and stop date. In addition, start time will be collected for events beginning on the day of the first injection.

Medical conditions or diseases present before a subject is enrolled in the study are only considered AEs if they worsen after the subject is enrolled.

For each AE, the seriousness, severity, and causal relationship to study drug will be assessed and entered in the source document. All items on the AE page of the eCRF should be completed for each AE.

Surgical procedures themselves are not AEs; they are therapeutic measures for conditions that require surgery. The condition for which the surgery is required is an AE, if it occurs or is detected during the study period. Planned surgical measures and the conditions leading to these measures are not AEs, if the condition(s) was (were) known before the study treatment. In the latter case, the condition should be reported as medical history.

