### **5.2. Secondary Objectives**

The secondary objectives of this study are to:

- Evaluate the safety and tolerability of leuprolide acetate 45 mg for injectable suspension in children with CPP;
- Characterize the burst kinetics of leuprolide acetate 45 mg after the first administration;
- Characterize the pharmacodynamic (PD) relationship of leuprolide serum concentrations to concentrations of serum luteinizing hormone (LH), follicle stimulating hormone (FSH) and testosterone/estradiol;
- Assess percent change from baseline in height and bone age after the first treatment administration;
- Assess growth velocity of height in cm/year after the first treatment administration;
- Assess changes in physical signs of puberty as measured by changes in Tanner stages or in changes or onset of menses; and
- Determine the dosing interval (5 or 6 months) at which leuprolide acetate is able to suppress LH concentration to <4 mIU/mL (after gonadotropin releasing hormone agonist [GnRHa] stimulation test) as data permits.

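### Coded adverse events are not summarised by injection, time since injection or exposure, so the onset of events such as early vaginal bleeding would show only in listings

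*SAP*

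**What the plan says.** **Coded adverse events.** SAP 14.4 states: "Number and percent of subjects reporting AEs will be tabulated for the Safety population". It continues: "Summaries will be presented by System Organ Class (SOC) and Preferred Term (PT), and further by severity and relationship to the investigational product". In the severity tables a child with several events under the same class or term "will be counted only once under the strongest severity"; in the relationship tables the child "will be counted only once under each applicable relationship". Table 5 footnote 4 repeats these rules. SAP 14.4.2 (serious events) and 14.4.3 (events leading to discontinuation) likewise count each child once per preferred term over the treatment period. Protocol 9.2.6 plans the same kind of table for adverse events, although it divides continuous laboratory results by treatment cycle and vital signs by treatment period.

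**Timing of the known effect.** Protocol 6.1 says: "During the first weeks of treatment, clinical signs of puberty, such as vaginal bleeding, may occur". It adds that such signs may persist past the second month.

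**What is analysed by time.** Protocol 8.5.1 introduces a question put two weeks after each injection and at each visit, "In order to evaluate changes in the acute (within two weeks of administration) and chronic hormonal responses associated with GnRH antagonist treatments over time". SAP 8.2.3 reports the resulting checklist by time point. It compares the first injection with later ones, and post-injection windows with pre-visit windows.

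**Data available.** Protocol 8.5.5: "The information recorded for AEs will include start date". Protocol 8.3.4.2 has the date and time of each injection recorded.

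**The concern.** A secondary objective is to "Evaluate the safety and tolerability of leuprolide acetate 45 mg for injectable suspension in children with CPP". For a depot with an expected initial flare, the natural safety questions are when an event begins after an injection, whether it recurs after later injections, and how many children were under observation at the time. A cumulative percentage per term answers none of these. Two children with the same term, one with onset in Week 2 and one in Month 11, add the same amount to the same cell.

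The percentage is also hard to interpret when follow-up differs by design. For events that go on accruing, early stops lower it and a Part B extension raises it, with no change in the underlying risk. The Visit 3 stop is triggered by lack of LH suppression, so the children with short follow-up are not a random subset.

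**Working it through.** **1. Does another planned summary give the timing?**

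| Source | Timed? | Covers vaginal bleeding or pubertal signs? |
|---|---|---|
| Adverse event tables (SAP 14.4, Table 5 footnote 4; protocol 9.2.6) | No | Yes, if reported as an adverse event |
| Checklist (SAP 8.2.3, Appendix 3) | Yes | No: flare or hot flashes, injection site reactions, urination, bone pain, weakness, allergic reactions |
| Tanner stage and menses (SAP Table 5) | By visit | Yes, but only at Screening and then from Visit 3 (Week 12) |
| Adverse event listings (protocol 9.2.6) | Start and stop dates | Yes, but with no denominator |

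Bleeding in the first weeks therefore reaches a summary table only through the untimed one.

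**2. Is the checklist row itself complete?** The flare row of SAP Table 5 names the Week 26 and Week 46 calls and Visits 2 to 11. Injections fall at Weeks 0, 24, 44 and 64, so the calls are at Weeks 2, 26, 46 and 66. The row omits Weeks 2 and 66. At nominal timing, Visit 2 (Week 4) looks back over Weeks 2 to 4, so the fortnight after Injection #1 is absent from the row. SAP 8.2.3 uses that fortnight as the reference for its comparison with later injections.

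**3. How unequal is follow-up?**
- About 12 weeks for children stopped at Visit 3 (protocol 8.6.5). This is not a minimum, because earlier withdrawal is possible. Serious events are reported to 6 months after the last dose (5 months in Part B).
- 48 weeks in Part A (protocol 8.1.1).
- 80 weeks only if Part B is invoked (protocol 8.6.18), with about 27 children expected to reach Month 21 (protocol 8.1.2). Visits up to Month 16 follow 4-week months, which would put Month 21 at Week 84. The printed label needs reconciling; Week 80 is used here.

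**4. Effect on a crude percentage.** The documents give no adverse event rate, so there is no planned figure to reproduce and the risks below are assumptions. With constant hazard h per week, risk at week t is F(t) = 1 − exp(−ht), with h = −ln(1 − c)/48 for an assumed 48-week risk c.

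For c = 20%, h = 0.2231/48 = 0.00465, or 24.2 per 100 person-years. Then F(12) = 5.4%, F(48) = 20.0% and F(80) = 31.1%.

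Pooled percentages for 60 children (the planned enrolment; the dosed number may be smaller):
- Part A only, 30% stopping at Week 12: (18 × 5.4% + 42 × 20.0%)/60 = 15.6%. With none stopping: 20.0%.
- Part B, 27 to Week 80 and 33 to Week 48: (27 × 31.1% + 33 × 20.0%)/60 = 25.0%.
- Part B, 27 to Week 80 and 33 stopping at Week 12 (an extreme mix): (27 × 31.1% + 33 × 5.4%)/60 = 17.0%.

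| Assumed 48-week risk | Part A only, 30% to 0% stopping | Part B, two mixes |
|---|---|---|
| 10% | 7.8% to 10.0% | 8.7% to 12.7% |
| 20% | 15.6% to 20.0% | 17.0% to 25.0% |
| 40% | 31.6% to 40.0% | 32.4% to 47.8% |

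**5. The front-loaded case.** An event confined to the first weeks with 20% risk gives 20% at 12, 48 or 80 weeks. With everyone followed for 48 weeks, the crude table cannot tell it from the constant-hazard event above. A person-time rate alone does not solve this. The same 20% becomes 0.20/(12/52) = 86.7, 0.20/(48/52) = 21.7 or 0.20/(80/52) = 13.0 per 100 person-years, depending only on follow-up.

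**The case against.** The strongest reply is that the flare is already analysed by time. The checklist is prespecified, is asked after every injection and at every visit, and is compared across injections. A reader might infer from SAP 14.4 that early flare and later events are simply merged. For the checklist items that is not so. The reply fails for coded events outside the checklist, including the protocol's own example, vaginal bleeding.

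Second, the listings show timing. Protocol 9.2.6 lists start dates, SAP 14.4 lists treatment-emergent events by subject, and a footnote to Table 5 promises listings of all collected values. With about 60 children a reader could reconstruct the onset pattern. That stands, but a listing does not supply the number of children still followed in each interval.

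Third, a late event might be thought to hide loss of suppression. The documents do not support that reading, because suppression is measured directly by stimulated LH at scheduled visits.

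Fourth, a reader might argue that the dosing-interval objective requires tolerability at 5 and 6 months to be separated. That objective concerns LH below 4 mIU/mL. The case for splitting adverse events rests on the safety objective alone.

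Finally, safety is descriptive, there is one arm, and a crude incidence table is a legitimate main display. All of that stands. The mock tables (SAP Appendix 5) are marked as still to come, so a split might yet be planned there, but the SAP text does not call for one.

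**Conclusion.** The gap is real and modest. The coded adverse event tables carry no information on injection, onset or exposure, and the timed checklist does not cover the pubertal signs that protocol 6.1 ties to early treatment.

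Three stronger readings should be avoided. Children are not counted once for the whole study: the rule is once per class or term, and possibly under more than one relationship. Follow-up does not run to 80 weeks unless Part B is invoked; otherwise it is about 12 to 48 weeks. Unequal follow-up biases no comparison between arms, because there is only one; it affects how the percentages are read.

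The size rests on assumed constant hazards and assumed mixes of follow-up. In Part A alone the 20% example falls by at most 4.4 percentage points (20.0% to 15.6%) even with 30% stopping at Week 12. For a purely early event, follow-up length beyond the first weeks hardly matters, and the loss is of onset information only. No efficacy claim or adaptation decision depends on this point.

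**What to change.** Keep the overall table and add the following.

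1. In SAP 14.4, tabulate treatment-emergent events by class and term, injection number, and onset interval after that injection. Use the protocol's own two-week window for the first interval (0 to 2 weeks). The sponsor should set the later intervals in advance, up to the next injection or last visit.
2. As denominator, use the children dosed at that injection and still followed at the start of the interval, and print it in each column.
3. Give an exposure-adjusted rate by injection period as a supplement only, for the reason in step 5 of the working. State that 6-month and 5-month periods are not to be compared as an effect of interval: the first-dose flare always falls in a 6-month period.
4. Flag events with imputed start dates. SAP 12 may replace a missing day by the dose date when month and year match, which would move such events into the first interval.
5. Reconcile the flare row of SAP Table 5 with SAP 8.2.3, which needs the call after every injection.

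The cost is one extra table from dates already collected and a one-row correction. No visit, dose or clinical rule changes. The drawback is sparse cells, particularly after Injections #3 and #4.
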